6.5.3.5. Dose Interruptions

Applicable to axitinib.

An interruption is defined a 0 mg dose administered on one or more days for axitinib. What follows defines how dose interruptions will be counted in the case of multiple dose interruptions.

- If an interruption occurs consecutively for at least two days due to the same reason, then it will be counted only once (example: If the actual dose on Days 1-3 is 10 mg and actual dose on Days 4-5 is 0 mg and dose interruption on Days 4-5 is due to AE, then the total number of dose interruptions is 1).

- If an interruption occurs consecutively for at least two days due to different reasons, then it will be counted for each reason (example: If the actual dose on Days 1-3 is 10 mg and actual dose on Days 4-5 is 0 mg and dose interruption on Day 4 is due to AE and dose interruption on Day 5 is due to dosing error, then the total number of dose interruptions is 2).
- If an interruption occurs for more than one day due to the same reason, but the days are not consecutive, ie, there is at least one dosing day in between, then each dose interruption will be counted as a different occurrence (example: If the actual dose on Days 1, 3 and 5, is 10 mg and actual dose on Days 2 and 4 is 0 mg, and dose interruptions on Day 2 and 4 are both due to dosing error, the total number of dose interruptions is 2).

A dose interruption is not considered a dose reduction.

The number and percentage of patients with dose interruptions and the corresponding reasons will be summarized.

6.5.3.6. Dose Delays

Applicable to avelumab.

Dose Delay is the difference between the actual time between two consecutive non-zero doses and the planned time between the same two consecutive non-zero doses.

Dose Delay for Dose x (days) = Date of Dose x – Date of Dose (x-1) – 14.

Dose delays will be grouped into the following categories:

- No delay;
- 1-3 days delay;
- 4-6 days delay;
- 7 or more days delay.

For example, for avelumab, administered on a 2-week schedule, if one patient receives avelumab on Day 1, then the next avelumab administration date will be on Day 15; however, if the patient receives avelumab at Day 16, 17 or 18, this is considered as 1-3 days delay.

No delay and 1-3 days delay will also be summarized together.

The number and percentage of patients with delayed study drug administration and maximum length of delay, ie, the worst case of delay if patients have multiple dose delays will be summarized.

6.5.3.7. Infusion Rate Reductions

Applicable to avelumab.

The number and percentage of patients with at least one infusion rate reduction of $\geq 50\%$ compared to the first infusion rate reported in the eCRF as well as the frequency of patients with 1, 2, 3 or ≥ 4 infusion rate reductions of $\geq 50\%$ will be summarized.

6.5.3.8. Infusion Interruptions

Applicable to avelumab.

An infusion interruption is defined as an infusion that is stopped and re-started on the same day (ie, for a visit more than one infusion start time and infusion end time are recorded).

The number and percentage of patients with at least one infusion interruption as well as the frequency of patients with 1, 2, 3, or ≥ 4 infusion interruptions will be summarized.

6.5.4. Concomitant Medications and Non-drug Treatments

The following analyses will be based on the safety analysis set by treatment group.

Concomitant medications are medications, other than study medications, which started prior to first dose date of study treatment and continued on on-treatment period as well as those started during the on-treatment period. **Prior medications** are medications, other than study medications and pre-medications for study drug, which are started before the first dose of study treatment.

Prior and concomitant medications will be summarized from the 'General Concomitant Medications' eCRF page. Pre-medications for study drug will also be summarized separately from the 'Pre-Medication Treatment' eCRF page.

Summary of prior medications, summary of concomitant medications and summary of pre-medications will include the number and percentage of patients by Anatomical Therapeutic Chemical (ATC) Classification level 2 and preferred term. A patient will be counted only once within a given drug class and within a given drug name, even if he/she received the same medication at different times. If any prior or concomitant medication is classified into multiple ATC classes, the medication will be summarized separately under each of these ATC classes. The summary tables will be sorted on decreasing frequency of drug class and decreasing frequency of drug name in a given drug class. In case of equal frequency regarding drug class (respectively drug name), alphabetical order will be used. In case any specific medication does not have ATC classification level 2 coded term, it will be summarized under 'Unavailable ATC classification' category.

A listing of prior medications and a listing of concomitant medications will be created with the relevant information collected on the 'General Concomitant Medications' eCRF page. A listing of pre-medications will be created with the relevant information collected on the 'Pre-Medication Treatment' eCRF page.

All concurrent procedures, which were undertaken any time during the on-treatment period, will be listed according to the eCRF page ‘General Non-drug Treatments’.

A listing of concurrent procedures will be created with the relevant information collected on the ‘General Non-drug Treatments’ eCRF page.

6.5.5. Subsequent Anti-cancer Therapies

The following analyses will be based on the FAS by treatment group.

Anti-cancer treatment will be provided in a data listing with data retrieved from ‘Follow-up Cancer Therapy’ eCRF page, eCRF pages related to the follow-up non-drug locoregional treatments, ‘Concomitant Radiation Therapy’, ‘Follow-up Radiation Therapy’, ‘Concomitant Surgery’, and ‘Follow-up Surgery’ eCRF pages.

Number and percentage of patients with any anti-cancer therapy after discontinuation will be tabulated overall and by type of therapy based on the data collected from the ‘Follow-up Cancer Therapy’ eCRF page, eCRF pages related to the follow-up non-drug locoregional treatments, ‘Follow-up Radiation Therapy’ and ‘Follow-up Surgery’ eCRF pages.

Number and percentage of patients with 2nd line systemic or locoregional treatment will be tabulated by type of therapy based on the data collected from the ‘Follow-up Cancer Therapy’ eCRF page and eCRF pages related to the follow-up non-drug locoregional treatments.

6.6. Safety Summaries and Analyses

The Safety Analysis Set will be the primary population for safety evaluations. Summaries of AEs and other safety parameters will be based on the safety analysis set by treatment group.

6.6.1. Adverse Events

Treatment-emergent adverse events (TEAEs) are those events with onset dates occurring during the on-treatment period for the first time, or if the worsening of an event is during the on-treatment period as defined in [Section 3.5.1](#).

All analyses described will be based on TEAEs (started during the on-treatment period) if not otherwise specified. The AE listings will include all AEs (whether treatment-emergent or not). AEs outside the on-treatment period will be flagged in the listings.

- **Related Adverse Events:** adverse events with relationship to study treatment (as recorded on the AE eCRF page, Relationship with study treatment = Related) reported by the investigator and those of unknown relationship (ie, no answer to the question ‘Relationship with study treatment’). Related AEs are those related to any study drug (ie, at least one of the study drugs).
- **Serious Adverse Events (SAE):** serious adverse events (as recorded on the AE eCRF page, Serious Adverse Event = Yes).

- **Adverse Events Leading to Dose Reduction:** adverse events leading to dose reduction of study treatment (as recorded on the AE eCRF page, Action taken with study treatment = Drug reduced).
- **Adverse Events Leading to Interruption of Study Treatment:** adverse events leading to dose interruption of study treatment (as recorded on the AE eCRF page, Action taken with study treatment = Drug interrupted). The eCRF does not allow for a clear separation between interruption of an infusion and delays of administration for a parenteral drug as both are recorded using the same term on the eCRF (“Drug interrupted”). IRRs will be excluded in the analysis of AEs leading to Drug Interruption in case they only led to an interruption of the infusion.
- **Adverse Events Leading to Permanent Treatment Discontinuation:** adverse events leading to permanent discontinuation of study treatment (as recorded on the AE eCRF page, Action taken with study treatment = Drug withdrawn).
- **Adverse Events Leading to Death:** adverse event leading to death (as recorded on the AE eCRF page, Outcome = Fatal, as well as AEs of Grade 5).
- **Immune-related Adverse Events (irAE):** irAEs (as identified according to the methodology outlined in [Appendix 1](#) for a pre-specified search list of MedDRA PTs, documented in the Safety Review Plan and finalized for analysis of the current studies data prior to DB lock).
- **Infusion-related Reactions (IRR):** IRRs (as identified according to the methodology outlined in [Appendix 2](#) for a pre-specified search list of MedDRA PTs documented in the Safety Review Plan and finalized for analysis of the current studies data prior to DB lock).

Unless otherwise specified, AEs will be summarized by number and percentage of patients with the AE in the category of interest as described above, by treatment group, primary SOC and PT in decreasing frequency based on the frequencies observed for the avelumab 10 mg/kg in combination with axitinib 5 mg group.

Each patient will be counted only once within each SOC or PT. If a patient experiences more than one AE within a SOC or PT for the same summary period, only the AE with the strongest relationship or the worst severity, as appropriate, will be included in the summaries of relationship and severity.

6.6.1.1. All Adverse Events

Adverse events will be summarized by worst severity (according to NCI-CTCAE v.4.03) per patient, using the latest version of MedDRA preferred term (PT) as event category and MedDRA primary system organ class (SOC) body term as Body System category.

In case a patient has events with missing and non-missing grades, the maximum of the non-missing grades will be displayed. No imputation of missing grades will be performed.

The following tables will be created:

- The overall summary of AEs table will include the frequency (number and percentage) of patients with each of the following by treatment group:
 - TEAEs;
 - TEAEs, Grade ≥ 3 ;
 - Related TEAEs;
 - Related TEAEs, Grade ≥ 3 ;
 - TEAEs leading to dose reduction of avelumab;
 - TEAEs leading to dose reduction of axitinib;
 - TEAEs leading to interruption of avelumab;
 - TEAEs leading to interruption of axitinib;
 - TEAEs leading to discontinuation of avelumab;
 - TEAEs leading to discontinuation of axitinib;
 - TEAEs leading to discontinuation of any study drug;
 - TEAEs leading to discontinuation of all study drugs;
 - Related TEAEs leading to discontinuation of avelumab;
 - Related TEAEs leading to discontinuation of axitinib;
 - Related TEAEs leading to discontinuation of any study drug;
 - Related TEAEs leading to discontinuation of all study drugs;
 - Serious TEAEs;
 - Related Serious TEAEs;
 - TEAEs leading to death;
 - Related TEAEs leading to death;
 - irAEs;
 - IRRs.

- TEAEs by SOC and PT and worst grade;
- Related TEAEs by SOC and PT and worst grade;
- TEAEs leading to death by SOC and PT;
- Related TEAEs leading to death by SOC and PT;
- TEAEs by SOC and PT: displaying in separate columns the All TEAEs / Related TEAEs / Grade ≥ 3 TEAEs / Related Grade ≥ 3 TEAEs;
- TEAEs Excluding SAEs, with frequency $\geq 5\%$ in any treatment group by SOC and PT.

6.6.1.2. Adverse Events Leading to Dose Reduction

The frequency (number and percentage) of patients with each of the following will be presented for TEAEs leading to dose reduction of each study drug by treatment group:

- TEAEs leading to dose reduction of avelumab by SOC and PT;
- TEAEs leading to dose reduction of axitinib by SOC and PT.

The listing of all AEs leading to dose reduction will also be provided with the relevant information.

6.6.1.3. Adverse Events Leading to Interruption of Study Treatment

The eCRF does not allow for a clear separation between interruption of an infusion and delays of administration for a parenteral drug as both are recorded using the same term on the eCRF (“Drug interrupted”). IRRs will be excluded in the analysis of AEs leading to Drug Interruption in case they only led to an interruption of the infusion (ie, did not lead to a dose reduction or a dose delay).

As such, AEs leading to interruption will be defined as AEs identified in the AE eCRF page with an action taken with study treatment of ‘drug interrupted’ excluding

- IRRs that occurred on the day of infusion with $\geq 90\%$ of the planned dose given (ie, IRRs that did not lead to a dose reduction) and subsequent administration of study drug had no delay (as defined in [Section 6.5.3.6](#)). These IRRs will be considered as IRRs leading to interruption of infusion.
- IRRs occurring on the day after infusion and subsequent dose administration had no delay (as defined in [Section 6.5.3.6](#)).

The frequency (number and percentage) of patients with each of the following will be presented for TEAEs leading to interruption of each study drug by treatment group:

- TEAEs leading to interruption of avelumab by SOC and PT;

- TEAEs leading to interruption of axitinib by SOC and PT.

The listing of all AEs leading to interruption of study treatment will also be provided with the relevant information.

In addition, the frequency (number and percentage) of patients with each of the following will be presented for TEAEs leading to interruption of each study drug by treatment group:

- TEAEs leading to both interruption and dose reduction of avelumab by SOC and PT;
- TEAEs leading to both interruption and dose reduction of axitinib by SOC and PT.

This summary will take into account PTs with both actions as defined in [Section 6.6.1](#), eventhough the actions may be captured for different PT records (ie, different onset for the PT with action “drug interrupted” and the PT with action “dose reduced”).

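### The exclusion for paused avelumab infusions sits in a definition that also feeds the axitinib interruption table, so read literally it drops some infusion reactions for which axitinib was held

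*SAP*

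**What the plan says.** SAP 6.6.1.3 opens with a data-capture problem: "The eCRF does not allow for a clear separation between interruption of an infusion and delays of administration for a parenteral drug". From this it draws a principle: "IRRs will be excluded in the analysis of AEs leading to Drug Interruption in case they only led to an interruption of the infusion". A parenthesis then explains that condition as meaning no dose reduction and no dose delay. SAP 6.6.1 states the same principle, without the parenthesis and without any bullets.

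The working definition follows: "As such, AEs leading to interruption will be defined as AEs identified in the AE eCRF page with an action taken with study treatment". The action in question is drug interrupted, and two classes of IRR are taken out:

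- IRRs on the day of infusion, if at least 90% "of the planned dose given (ie, IRRs that did not lead to a dose reduction) and subsequent administration of study drug had no delay";
- "IRRs occurring on the day after infusion and subsequent dose administration had no delay".

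Both bullets take the meaning of delay from SAP 6.5.3.6, which is marked "Applicable to avelumab" and begins: "Dose Delay is the difference between the actual time between two consecutive non-zero doses". Neither bullet asks which drug was interrupted. Two tables follow from the definition, one for avelumab and one for axitinib ("TEAEs leading to interruption of axitinib by SOC and PT"). The same section also plans a table for each drug of events that led to both interruption and dose reduction.

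For axitinib, SAP 6.5.3.5 defines an interruption as one or more days at 0 mg and says that this is not a dose reduction. Protocol 5.4.5 allows the two drugs to be modified independently.

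**The concern.** The reason for the exclusion applies to an infused drug. The exclusion itself is written for every record of drug interrupted, and it is tested with avelumab information alone. An axitinib hold is neither a reduction nor a delay of avelumab, so an IRR that led to such a hold can pass every test in the bullets and leave the axitinib table.

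The day-after bullet shows this most clearly. An event that starts the day after a one-hour infusion cannot have paused that infusion, and the no-delay condition means that the next avelumab dose was on time. For a day-after IRR that meets the bullet, a real interruption could therefore only be one of axitinib.

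Tolerability of the combination is the primary objective. TEAEs leading to axitinib interruption form a row of the overall AE summary in SAP 6.6.1.1, which SAP 6.1.1.1 makes part of the primary analysis, and have their own table by SOC and PT. Any error from this rule goes one way: it can lower the axitinib count but never raise it.

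**Working it through.** **The rule.** Take an IRR for which the recorded axitinib action is drug interrupted. Apply the two bullets as written, then apply them only to avelumab records.

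| IRR onset | At least 90% of avelumab dose given | Next infusion delayed | In axitinib table, as written | In axitinib table, exclusion limited to avelumab |
|---|---|---|---|---|
| Infusion day | Yes | No | **No** | Yes |
| Infusion day | Yes | Yes | Yes | Yes |
| Infusion day | No | No | Yes | Yes |
| Infusion day | No | Yes | Yes | Yes |
| Day after | Yes | No | **No** | Yes |
| Day after | Yes | Yes | Yes | Yes |
| Day after | No | No | **No** | Yes |
| Day after | No | Yes | Yes | Yes |

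As written, the event is lost in 3 of the 8 combinations. With the exclusion limited to avelumab it is lost in none. The 3 of 8 counts logical cases and is not a frequency.

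**Inputs for scale.** N = 20 (SAP 5.1.1). IRRs were reported in 7 of 47 patients, 14.9%, in the earlier combination study (Protocol 1.2.4); 7/47 = 0.149 reproduces that figure. The documents give no frequency of axitinib holds for IRRs, so the share h of IRR patients who hold axitinib is an assumption and is varied.

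**One patient.** 1/20 = 5 percentage points of the overall row. The row counts patients, so it falls only if the patient has no other TEAE leading to axitinib interruption. The same holds for each SOC or PT row, with respect to other interrupting events in that row.

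**Expected loss.** Assume the 7/47 rate carries over, every such IRR meets an exclusion, and none of these patients has another axitinib-interrupting TEAE. The last two assumptions push the result upward. With q = (7/47) × h:

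- expected patients removed = 20 × q;
- expected fall = 100 × q percentage points;
- probability that at least one patient is removed = 1 − (1 − q)^20.

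| h | Expected patients removed | Expected fall (points) | Probability of at least one removed |
|---|---|---|---|
| 5% | 0.15 | 0.7 | 0.139 |
| 10% | 0.30 | 1.5 | 0.259 |
| 25% | 0.74 | 3.7 | 0.532 |
| 50% | 1.49 | 7.4 | 0.787 |
| 100% | 2.98 | 14.9 | 0.960 |

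The expected fall stays below 5 points as long as h is below 5/14.9, about one third.

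**Design figure.** The plan's only design probability, 88% for seeing at least one AE of 10% incidence in 20 patients, reproduces as 1 − 0.9^20 = 0.878. This point does not affect it.

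**The case against.** The best reply is that the governing principle already protects the axitinib table. Only IRRs that did nothing more than interrupt the infusion are to be excluded, the reason given concerns a parenteral drug, and the bullets are introduced as carrying that principle out. An IRR that led to an axitinib hold did more than interrupt an infusion. This stands as evidence of intent, and a careful programmer might apply it. But SAP 6.6.1.3 explains the condition as no dose reduction and no dose delay, which an axitinib hold does not breach, and the bullets name no drug. Nor does the SAP say whether the overall row and the combined interruption-and-reduction tables follow the bullets or the shorter text of 6.6.1, which the combined tables cite. The two could give different counts.

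Other replies limit the size, and they stand:

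- Protocol Table 2 advises an unchanged axitinib dose for IRRs of Grades 1 to 4, so a hold for an IRR would depart from guidance. It remains possible: SAP Appendix 2 assigns IRRs by program from PT and timing, so an event that the investigator attributed to axitinib can still be classed as one.
- Day-after events qualify as IRRs only through the core PT list (Table 12, condition 4B), which is a narrow class.
- Table 2 provides for axitinib holds for other toxicities, so some affected patients would be counted anyway.
- The 7/47 rate comes from renal cell carcinoma patients and a reported TEAE term, not from the Appendix 2 algorithm.
- The SAP has no hypothesis test and no decision rule that depends on this count.

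A reader might also infer that the day-after bullet serves no purpose. The text does not support that: for avelumab it can remove a drug-interrupted entry where no dose was in fact delayed.

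**Conclusion.** The point holds as a defect of wording with a possible effect on a primary safety count. As written, SAP 6.6.1.3 drops an IRR with axitinib held from the axitinib table in two situations: onset on the infusion day with at least 90% of the avelumab dose given and no delay of the next infusion, or onset the day after with no delay of the next infusion.

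The effect is one-directional and probably small. Assuming the 7/47 rate, the expected fall in the overall row ranges from 0 to at most about 15 points and is most likely 0 to 5. The lower part of the range is a judgement based on the Table 2 advice, not on data.

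Three stronger readings are tempting, and the documents do not support them:

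- *Every such IRR is lost whenever avelumab is on time.* This is true for day-after IRRs only. Infusion-day IRRs also need at least 90% of the dose given.
- *Each affected patient costs 5 points.* This is so only for a patient with no other TEAE leading to axitinib interruption.
- *The plan conceals axitinib holds.* The hold still enters the exposure summary of axitinib interruptions and their reasons (SAP 6.5.3.5), the IRR still appears in the tables and listing of SAP 6.6.4, and the general AE listings cover all AEs. The practical consequence is that the exposure table and the AE table could disagree on axitinib interruptions due to AEs.

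**What to change.** State in SAP 6.6.1 and 6.6.1.3 that both IRR exclusions apply only to records where the action of drug interrupted is for avelumab, and only to the avelumab tables. For axitinib, count every TEAE whose recorded axitinib action is drug interrupted, IRRs included. Apply the same limit to the overall summary rows and to the tables of events with both interruption and dose reduction.

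The cost is about one sentence in each section and one programming condition. No new data are needed, provided the AE page records the action for each drug separately, which the planned drug-specific tables already require. The sample size and the other analyses are unaffected.

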6.6.1.4. Adverse Events Leading to Discontinuation of Study Treatment

The frequency (number and percentage) of patients with each of the following will be presented for TEAEs leading to permanent discontinuation of each study drug and study treatment, by treatment group:

- TEAEs leading to discontinuation of avelumab by SOC and PT;
- Related TEAEs leading to discontinuation of avelumab by SOC and PT;
- TEAEs leading to discontinuation of axitinib by SOC and PT;
- Related TEAEs leading to discontinuation of axitinib by SOC and PT;
- TEAEs leading to discontinuation of any study drug by SOC and PT;
- Related TEAEs leading to discontinuation of any study drug by SOC and PT;
- TEAEs leading to discontinuation of all study drugs by SOC and PT;
- Related TEAEs leading to discontinuation of all study drugs by SOC and PT.

The listing of all AEs leading to treatment discontinuation will also be provided with the relevant information.

